14.0 Setting

14.1 *Describe all facilities/sites where you will be conducting research procedures. Include a description of the security and privacy of the facilities (e.g. locked facility, limited access, privacy barriers). Facility, department, and type of room are relevant. Do not abbreviate facility names.*

NOTE: Examples of acceptable response may be: "A classroom setting in the Department of Psychology equipped with a computer with relevant survey administration software," "The angiogram suite at Buffalo General Medical Center, a fully accredited tertiary care institution within New York State with badge access," or, "Community Center meeting hall."

Response:

This research will be conducted at the University at Buffalo (UB), in the the Division of Behavioral Medicine Research Labs, located in G56, G58, G90, G96 and 151 Farber Hall, University at Buffalo South Campus.

14.2 For research conducted outside of UB and its affiliates, describe:

- Site-specific regulations or customs affecting the research
- Local scientific and ethical review structure

NOTE: This question is referring to UB affiliated research taking place outside UB, i.e. research conducted in the community, school-based research, international research, etc. It is not referring to multi-site research. UB affiliated institutions include Kaleida Health, ECMC, and Roswell Park Cancer Institute.

Response:

N/A: This study is not conducted outside of UB or its affiliates.

15.0 Community-Based Participatory Research

15.1 Describe involvement of the community in the design and conduct of the research.

NOTE: Community-Based Participatory Research (CBPR) is a collaborative approach to research that equitably involves all partners in the research process and recognizes the unique strengths that each brings. CBPR begins with a research topic of importance to the community, has the aim of combining knowledge with action and achieving social change to improve health outcomes and eliminate health disparities.

Response:

N/A: This study does not utilize CBPR.

16.0 Resources and Qualifications

16.1 Describe the qualifications (e.g., education, training, experience, expertise, or certifications) of the Principal Investigator **and** staff to perform the research. When applicable describe their knowledge of the local study sites, culture, and society. Provide enough information to convince the IRB that you have qualified staff for the proposed research.

NOTE: If you specify a person by name, a change to that person will require prior approval by the IRB. If you specify a person by role (e.g., coordinator, research assistant, co-investigator, or pharmacist), a change to that person will not usually require prior approval by the IRB, provided that the person meets the qualifications described to fulfill their roles.

Response:

The Principal Investigator, [name] is a Distinguished Professor of Pediatrics, and Social and Preventive Medicine at the State University of New York at Buffalo. [name] has published over 300 papers in peer reviewed journals. The project coordinator and research staff have experience in behavioral research using similar methodology and have completed the appropriate certifications: CITI and CPR/First Aid/AED.

Describe other resources available to conduct the research.

16.2 Describe the time and effort that the Principal Investigator and research staff will devote to conducting and completing the research.

NOTE: Examples include the percentage of Full Time Equivalents (FTE), hours per week. The question will elicit whether there are appropriate resources to conduct the research.

Response:

The Principal Investigator will devote approximately 5-8 hours per week to meet with staff, oversee data safety and discuss recruitment and study specific information.

The Project Coordinator will spend approximately 30% of their time training and supervising staff, including conducting weekly project meetings, 20% coordinating the scheduling of appointments for staff and prospective subjects, 10% coordinating and assisting in the test sessions, and 10% overseeing the development of study materials.

Research Assistants/Interventionists will spend approximately 50% of their time training and running participants, 20% recruiting subjects, 20% developing project materials, including questionnaires, surveys, and forms, and 10% entering data and quality control of the data collected during the study.

16.3 Describe the availability of medical or psychological resources that subjects might need as a result of anticipated consequences of the human research, if applicable.

NOTE: One example includes: on-call availability of a counselor or psychologist for a study that screens subjects for depression.

Response:

We do not anticipate a need for medical or psychological resources stemming from the research procedures. However, if during any of the visits, the participant discloses occurrences of recent life events that appear to cause the participant a high degree of distress (e.g., the participant is crying, appears in shock, etc.) the project coordinator and PI will be notified. These participants will be provided with a list of resources. Additionally, we will follow up with the participant within the next 24 hours of said occurrence.

16.4 Describe your process to ensure that all persons assisting with the research are adequately informed about the protocol, the research procedures, and their duties and functions.

Response:

All personnel working on the project are required to complete the CITI training as required by IRB. Additionally, there are extensive procedures manuals that are

read and followed by all personnel. The Project Coordinator is responsible for training staff on data collection and recording procedures.

Project coordinator and the principal investigators will be responsible for ensuring proper staff training on study procedures and consistency of data collection between each site. This will be achieved through local training, regular communication between sites and coordinating procedural materials for experimenters.

17.0 Other Approvals

17.1 *Describe any approvals that will be obtained prior to commencing the research (e.g., school, external site, funding agency, laboratory, radiation safety, or biosafety).*

Response:

- N/A: This study does not require any other approvals.

18.0 Provisions to Protect the Privacy Interests of Subjects

18.1 *Describe how you will protect subjects' privacy interests during the course of this research.*

NOTE: Privacy refers to an individual's right to control access to him or herself. Privacy applies to the person. Confidentiality refers to how data collected about individuals for the research will be protected by the researcher from release. Confidentiality applies to the data.

Examples of appropriate responses include: "participant only meets with a study coordinator in a classroom setting where no one can overhear", or "the participant is reminded that they are free to refuse to answer any questions that they do not feel comfortable answering."

Response:

Prospective participants may contact the laboratory of their own free will and are thus controlling access to their privacy. All data will be collected in a secure laboratory environment in password protected databases in which only study staff has access. In sessions, participants will only interact with project research staff and sessions will take place in a private laboratory room that may include a closed circuit television monitoring system that will be monitored by the experimenter to ensure participant protocol adherence and safety. Participants are reminded that they are free to refuse to answer any questions that they do not feel comfortable answering and that all information is kept confidential to the extent provided by law.

The i2b2 data will be protected by only accessing identifiable contact information remotely on IHI's "virtual machine", so the identifiable data never leaves their secure encrypted server. All use of identifiable data is done behind the firewall on IHI's secure system.

In regards to the CDC procedures mentioned in the Procedures section:

In the case of a positive test of an infectious disease, any contact with the Person Under Investigation (PUI) will be disclosed to the Erie county health department as requested/required.

Erie county Department of Health, Epidemiology and Disease control includes forms for identifying reportable infectious diseases and contact information for the appropriate person at the Health department to discuss any personally identifiable information.

<http://www2.erie.gov/health/index.php?q=epidemiology-amp-disease-control>

18.2 Indicate how the research team is permitted to access any sources of information about the subjects.

*NOTE: Examples of appropriate responses include: school permission for review of records, consent of the subject, HIPAA waiver. This question **does apply** to records reviews.*

Response:

Participants will be recruited using a secure database of interested participants maintained by the Division of Behavioral Medicine and approved for use by previous IRB committees. Potential participants from this database will be contacted if they had indicated that they are willing to be contacted for participation in studies and thus control their own participation.

A HIPAA waiver has been completed for the recruitment of participants through medical records (i2b2, TriNetX, Urban Family Practice), which is completed through the physician's office with the consent of the primary care physician. The research team may also contact primary care physicians and pharmacists at their preferred pharmacy to confirm eligibility after participants have completed consent/HIPAA/medical/pharmacy release forms.

Any information through recruitment from Trialfacts will be deleted from there servers upon completion of the study and all information will be transferred to a secure database of interested participants maintained by the Division of Behavioral Medicine and approved for use by previous IRB committees. Potential participants from this database will be contacted if they had indicated that they are willing to be contacted for participation in studies and thus control their own participation.

19.0 Data Management and Analysis*

19.1 Describe the data analysis plan, including any statistical procedures. This section applies to both quantitative and qualitative analysis.

Response:

Pill count and MEMS data displayed as a percentage of doses taken will be displayed graphically to enable visual analysis of changes in means and trends of dependent variables across the different phases of the study.

Borckardt, J., & Nash, M. (2014). Simulation modelling analysis for small sets of single-subject data collected over time. *Neuropsychological Rehabilitation*, 24(3-4), 492–506. <https://doi.org/10.1080/09602011.2014.895390>

19.2 If applicable, provide a power analysis.

NOTE: This may not apply to certain types of studies, including chart/records reviews, survey studies, or observational studies. This question is asked to elicit whether the investigator has an adequate sample size to achieve the study objectives and justify a conclusion.

Response:

A power analysis is not applicable to this multiple baseline design. We are collecting weekly data from participants and will have enough data points to ensure we will be able to achieve the study objectives. The results of this study will be analyzed graphically as well as assessing the degree of change from baseline to treatment across the three replications. For an example of a study that utilized a multiple baseline design, see:

19.3 Describe any procedures that will be used for quality control of collected data.

Response:

The principal investigator will be responsible for ensuring data integrity and safety monitoring for human subjects who are involved in the research and communicating any negative outcomes of the data and safety monitoring plans (DSMP) reviews or any serious event or problem (SEP) that occur to the UB IRB and other required offices/agencies. Materials will be checked to make sure that all study data are coded with a unique participant ID. The ID will be linked only by a name through a master list kept by the project coordinator in a password-protected file.

20.0 Confidentiality*

A. Confidentiality of Study Data

Describe the local procedures for maintenance of confidentiality of study data and any records that will be reviewed for data collection.

20.1 A. Where and how will all data and records be stored? Include information about: password protection, encryption, physical controls, authorization of access, and separation of identifiers and data, as applicable. Include physical (e.g. paper) **and** electronic files.

Response:

The i2b2 data will be protected by only accessing identifiable contact information remotely on IHI's "virtual machine", so the identifiable data never leaves their secure encrypted server. All use of identifiable data is done behind the firewall on IHI's secure system.

Urban Family Practice patient data will be protected by only accessing identifiable contact information remotely. Urban Family Practice will send us an encrypted file, containing this contact information that will be stored on a password protected server that only the research staff will have access too.

Trialfacts recruitment data will be protected by only accessing survey information remotely. Trialfacts will send us an encrypted file/ Google spreadsheet, containing this information that will be stored on a password protected server that only the research staff will have access too.

Potential participants who have filled out the online screening survey will have their responses stored on a password protected server that only the research staff will have access too. Additionally, if there are paper copies of the screening survey responses they will be de-identified and stored in a locked filing cabinet in a locked room (G96/G56 Farber hall) which only research staff has access to.

Participants will be assigned a unique identification number to ensure the confidentiality of the data. A master list that links subject ID and participant's name will be kept in a secure file that is password protected on a password protected computer. Only research staff will access to the master list. Paper files (that may include forms such as: medical release/ pharmacy release forms and other study materials) will be kept in locked lab offices at the Division of Behavioral Medicine Research Lab and electronic files will be kept on password protected computers in password protected/encrypted databases only accessible to members of the research staff. When the results of the study are presented and/or published, only group data will be provided; no individual participant will be identifiable.

20.2 A. How long will the data be stored?

Response:

All study data will be retained for a period of at least three years. The master list linking the study ID with the participant name will be kept in a locked cabinet in G56 for three years after the completion of the study at which point it will be destroyed. Any identifiable information from participants (i.e. medical release forms/ pharmacy release forms) will be kept in a locked cabinet in G56 for three years after the completion of the study at which point it will be destroyed. De-identified data will be retained indefinitely. Information about potential participants provided to us by Urban Family Practice and Trialfacts will be deleted upon completion of the study.

20.3 A. Who will have access to the data?

Response:

Only the principal investigator and research staff associated with the study will have access to the data.

20.4 A. Who is responsible for receipt or transmission of the data?

Response:

The principal investigator takes primary responsibility for the data.

20.5 A. How will the data be transported?

Response:

Data will be transported in password protected/encrypted files via email. All transferred data will be de-identified.

B. Confidentiality of Study Specimens

Describe the local procedures for maintenance of confidentiality of study specimens.

- N/A:** No specimens will be collected or analyzed in this research.
(Skip to Section 21.0)

20.6 B. Where and how will all specimens be stored? Include information about: physical controls, authorization of access, and labeling of specimens, as applicable.

Response:

All and urine samples will be analyzed during session it is collected or immediately after the appointment and will not be saved (i.e., stored). Specimens will not be banked for future use.

20.7 *B. How long will the specimens be stored?*

Response:

N/A, specimens will not be stored

20.8 *B. Who will have access to the specimens?*

Response:

Research staff conducting appointments will have access to the specimens during or immediately after the appointment. However, specimens will not be stored.

20.9 *B. Who is responsible for receipt or transmission of the specimens?*

Response:

N/A, there is no receipt or transmission of the specimens.

20.10 *B. How will the specimens be transported?*

Response:

N/A, the specimens will not be transported.

21.0 Provisions to Monitor the Data to Ensure the Safety of Subjects*

- N/A: This study is not enrolling subjects, or is limited to records review procedures only. This section does not apply.

NOTE: *Minimal risk studies may be required to monitor subject safety if the research procedures include procedures that present unique risks to subjects that require monitoring. Some examples include: exercising to exertion, or instruments that elicit suicidality or substance abuse behavior. In such cases, N/A is not an acceptable response.*

21.1 *Describe the plan to periodically evaluate the data collected regarding both harms and benefits to determine whether subjects remain safe.*

Response:

Data will be reviewed weekly and secured in Division of Behavioral Medicine Research Lab. The Principal Investigator, [name], will be responsible for ensuring data integrity and safety monitoring for human subjects who are involved in the research and may work with a Data Safety Officer consistent with our NIH DSMP.

21.2 Describe what data are reviewed, including safety data, untoward events, and efficacy data.

Response:

Study questionnaires and measurements that are collected by study personnel will be reviewed and monitored.

21.3 Describe any safety endpoints.

Response:

This study poses no greater than minimal risk; therefore, there are no safety endpoints.

21.4 Describe how the safety information will be collected (e.g., with case report forms, at study visits, by telephone calls with participants).

Response:

Participants will be encouraged to contact study personnel if they experience any problems or difficulties, and if any adverse events (AE) are reported, the study personnel contacted will record the AE. AE will be recorded as soon as they are reported, and the PI and study coordinator will be made aware. The study coordinator will summarize the AE in a memo; the participant will be called and the summary will be read to them to ensure that the information is accurate. The memo will then be submitted to the University at Buffalo IRB and the PI. If the PI, or the IRB decide that further action is warranted, the PI and study coordinator will then formulate and carry out a plan to respond to the AE. The study coordinator will write a memo summarizing such actions; this memo will then be forwarded to the IRB. Safety information will be collected and reported to both the UBIRB and the Safety Officer in the time frames outlined by the UBIRB.

21.5 Describe the frequency of safety data collection.

Response:

Data will be reviewed weekly and secured in G56 and 252A Farber Hall. A weekly review of these data will be conducted by the principal investigator and project coordinator during their staff meetings with study personnel.

21.6 Describe who will review the safety data.

Response:

Serious Events and Problems (SEP) will be monitored by the principal investigator and project coordinator as well as reported to both the IRB and the Safety Officer in the timeframes outlined by the IRB.

21.7 Describe the frequency or periodicity of review of cumulative safety data.

Response:

Cumulative data will be reviewed approximately six months to a year based on the requirements of the Grant and NIH committee.

21.8 Describe the statistical tests for analyzing the safety data to determine whether harm is occurring.

Response:

N/A, there are no discontinuing criteria.

21.9 Describe any conditions that trigger an immediate suspension of the research.

Response:

N/A, there are no discontinuing criteria.

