2.0 Objectives*

2.1 Describe the purpose, specific aims, or objectives of this research.

Response:

Aim 1: To examine whether EFT improves medication adherence.

Aim 2: To test the influence of EFT on DD (Aim 2A), and PM (Aim 2B).

2.2 State the hypotheses to be tested, if applicable.

NOTE: A hypothesis is a specific, testable prediction about what you expect to happen in your study that corresponds with your above listed objectives.

Response:

Aim 1: We hypothesize that EFT will improve medication adherence.

Aim 2: We hypothesize that EFT will reduce DD and improve PM.

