We propose an RCT that will assess the effects of EFT on medication adherence, general PM, and DD among those with pre- or type 2 diabetes or related comorbidities who are currently taking at least one oral medication for diabetes or related comorbidities. We will recruit participants who are relatively non-adherent to an oral medication ($\leq 80\%$ of prescribed doses taken in the past month; to accommodate over-reporting) for prediabetes or type 2 diabetes or other conditions that commonly co-occur with these conditions (e.g., hypertension, hyperlipidemia). Medication adherence will be monitored using electronic pill bottle caps (MEMS caps, which record bottle openings with date and time stamps), pill counts, and pharmacy records. Medications for glucose control as well as control of hypertension and/or hyperlipidemia will be considered as targets for measurement. Participants self-rated as non-adherent ($\leq 80\%$ prescribed doses taken), and report difficulty remembering to take one’s medication as a primary reason for non-adherence, will undergo a 6 week, 8 week, or 10 week baseline period. After the staggered baseline periods, all participants will receive EFT intervention. In total, participants will be in baseline and treatment for a total of 15 weeks.

Randomized participants will complete bi-weekly in person sessions plus phone sessions for the weeks in which they do not come to the lab, in which they learn to engage in EFT for medication adherence. Initial EFT for medication adherence will focus on taking the targeted medication on a typical day (e.g., a weekday when the participant usually works), and in subsequent sessions EFT will be used to assist participants in adapting to unusual circumstances that may interrupt adherence or have been reported as contributing to non-adherence.

At an initial baseline session, post-intervention, and follow-up, participants will complete measures of working memory, lab-based PM, and DD. Dependent measures include change in targeted medication adherence (based on MEMS data), change in non-targeted medication adherence (for participants initially reporting non-adherence to multiple medications; based on self-report and pill count measures), DD, and PM. Moderators to be tested include working. The goal of the study will be to collect pilot data to test the feasibility and initial efficacy of the approach, as well as effect sizes for a subsequent R01.

4.2 Include complete citations or references.

Response:

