23.0 Risks to Subjects*

23.1 List the reasonably foreseeable risks, discomforts, hazards, or inconveniences to the subjects related to their participation in the research. Consider physical, psychological, social, legal, and economic risks. Include a description of the probability, magnitude, duration, and reversibility of the risks.

NOTE: Breach of confidentiality is always a risk for identifiable subject data.

Response:

There may be some sensitivity associated from certain questions asked when filling out questionnaires or having body measurements taken and subjects might feel uncomfortable disclosing some personal information such as medical history. Subjects can refuse to answer any questions that they are not comfortable answering. Subjects will be free to withdraw from the study at any time, and their refusal to continue will not affect other medical care provided at any healthcare facility.

Breach of confidentiality is another potential risk. To protect confidentiality, we will use only ID numbers and keep all data in locked cabinets or in locked offices and password protected electronic files in password protected computers.

There are no other risks anticipated. All personnel on the study will be CITI course certified and have completed the good research practices certification. All identifiable data will be password protected and only the research team will have access to that information. Subjects will be informed of the risks associated with the study.

23.2 Describe procedures performed to lessen the probability or magnitude of risks, including procedures being performed to monitor subjects for safety.

Response:

We have several provisions in place to ensure participants' privacy and safety is protected while the data is being collected. The lab facilities of the Division of Behavioral Medicine research laboratory consist of private interview rooms that will be used. Only the relevant research staff and participant will be present in the room during sessions. Data is recorded such that not even the person putting it in the file would ever be able to associate the data with the identity of the person providing it. Data and files that have been de-identified and encrypted will be shared between sites. Therefore, there is no reasonable risk of a breach of confidentiality.

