24.0 Potential Benefits to Subjects*

24.1 Describe the potential benefits that individual subjects may experience by taking part in the research. Include the probability, magnitude, and duration of the potential benefits. Indicate if there is no direct benefit.

NOTE: Compensation cannot be stated as a benefit.

Response:

Participants may benefit from improved health due to better adherence to their prescribed medication(s). Participants may also learn about the experimental research process and their health.

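### The intervention aims to raise actual intake of glucose, blood-pressure and lipid drugs, but 23.1 names no risk from greater drug effect and 21.4 relies on participants to report problems

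*Combined protocol and SAP*

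**What the plan says.** **Intended effect.** Section 2.2 states for Aim 1: "We hypothesize that EFT will improve medication adherence". Section 4.1 says "We will recruit participants who are relatively non-adherent to an oral medication", with a cut-off at or below 80% of prescribed doses (8.1 uses below 80%). On the drugs concerned, 4.1 adds: "Medications for glucose control as well as control of hypertension and/or hyperlipidemia will be considered as targets for measurement". Section 12.1 allows up to four electronic-cap bottles per participant, so intake of several drugs could rise together.

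**Benefit and risk.** Section 24.1 lists better health through improved adherence as a possible benefit. Section 23.1 lists discomfort with questions or body measurements, and breach of confidentiality, and then says: "There are no other risks anticipated".

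**Safety data.** Section 21.3 reads: "This study poses no greater than minimal risk; therefore, there are no safety endpoints". Section 21.4 gives the collection method: "Participants will be encouraged to contact study personnel if they experience any problems or difficulties". A reported event is recorded, passed to the principal investigator and coordinator, read back to the participant and sent to the IRB. Sections 21.1 and 21.5 provide a weekly data review. Section 21.2 says that it covers study questionnaires and measurements. Section 21.7 adds: "Cumulative data will be reviewed approximately six months to a year based on the requirements of the Grant and NIH committee".

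**The concern.** If the intervention works, participants take more active drug than they did at entry. Any unwanted effect of that would follow from the intended effect, so it is foreseeable. The protocol credits the mechanism with a benefit in 24.1 but does not mention its possible downside in 23.1.

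The collection method does not fill that gap. The prompt for 21.4 offers case report forms, visits and telephone calls as examples of how safety information might be gathered. The response describes none of them as a means of asking. It waits for the participant to make contact, although staff will already be talking to participants at sessions and calls.

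At stake are participant safety and what the pilot can say about tolerability when the follow-on grant is planned. A report of no events from 10 to 20 people, without systematic asking, would carry little information.

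**Working it through.** The plan states no event rate, safety sample size or safety analysis, so there is no safety figure to reproduce. The check has three parts.

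**1. Is an adverse-event enquiry specified anywhere in the available text?**
- Intervention sessions (12.1): self-reported and objective adherence. No adverse-event question.
- Assessment sessions (12.1): life events, memory and choice tasks, height and weight, adherence, reasons for non-adherence, reasons for opening bottles. No adverse-event question.
- Walk-through calls (12.1): practice with the cues. No adverse-event question.
- Data and instruments (12.2, 12.3): no adverse-event item, and no glucose or blood-pressure reading. Section 12.5 says no diagnostic tests are given.
- Weekly review (21.1, 21.2, 21.5): covers what has been collected, so it inherits these limits.

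The nearest solicited item is reasons for non-adherence. It could surface a side effect that led to missed doses. It would not systematically reach someone who now takes every dose and feels unwell.

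**2. What could incomplete capture do at this sample size?** Let n be participants, p the true proportion affected and c the fraction of affected participants whose event is recorded. Then P(no event recorded) = (1 − p·c)^n. Section 7.1 gives n as at least 10–12 randomized and up to 20 enrolled. Both p and c are assumptions.

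| n | p | c = 1 | c = 0.5 | c = 0.25 |
|---|---|---|---|---|
| 12 | 0.05 | 54% | 74% | 86% |
| 12 | 0.10 | 28% | 54% | 74% |
| 12 | 0.20 | 7% | 28% | 54% |
| 20 | 0.10 | 12% | 36% | 60% |

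For example, with n = 12 and p = 0.10: 0.90^12 = 0.28; 0.95^12 = 0.54; 0.975^12 = 0.74.

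Even with full capture, zero events leaves a one-sided 95% upper bound of 1 − 0.05^(1/n): 26% for n = 10, 22% for n = 12 and 14% for n = 20.

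**3. How do contacts compare between phases?** The totals in the 13.2 table reproduce if every EFT week has one call (0.20 h) and one session (0.58 h), on top of 0.5 + 2.5 + 2 × 2 = 7.0 h:
- 6-week group: 7.0 + 8 × 0.78 = 13.24 h
- 8-week group: 7.0 + 6 × 0.78 = 11.68 h
- 10-week group: 7.0 + 4 × 0.78 = 10.12 h

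That is 16, 12 and 8 EFT contacts. Section 4.1 instead has sessions alternating with calls, which gives 8, 6 and 4. On either reading there is at least one contact a week.

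In baseline, the table lists T1 in week 1 and T2 in week 6 or 8. Section 12.1 adds a week-6 adherence check, which under the COVID procedure is a mailbox cap collection. A question about the time since the last contact would therefore cover about five weeks or more in baseline, against one week or less during EFT.

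**The case against.** The strongest defence is that this is a small, minimal-risk behavioural pilot. It encourages medicines already prescribed, and intake rises at most to the existing prescription. Reported events are handled promptly and data are reviewed weekly. Some participants may have only a lipid drug as target. All of this stands and keeps the point modest. It does not supply a question that nobody is scheduled to ask, or a risk sentence that 23.1 lacks.

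A reader might infer several stronger things that the documents do not support:

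- **That harms are captured solely by volunteered report.** The measures attachment named in 12.3 and the monitoring plan cited in 21.1 are not available. A symptom item there would soften the point, though 21.4 should then cite it.
- **That safety review comes too late.** Recruitment of 4 months (7.3) or 6 months (13.1) plus 15 weeks (about 3.45 months) ends at about 7.45 or 9.45 months. A cumulative review at six months precedes both; only a later one might not. The weekly review runs throughout.
- **That the rise in doses taken measures the harm.** The documents give no mean baseline or expected adherence, and a ratio of doses says nothing about event frequency.
- **That the trial would report health benefit without its counterpart.** The endpoints are adherence, memory and decision-making. No glucose, HbA1c or blood-pressure outcome is planned, and 24.1 describes what participants may gain, not an analysis.

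**Conclusion.** The point holds as a gap in risk description and safety ascertainment. Section 23.1 omits a foreseeable consequence of the intended effect, and 21.4 specifies participant-initiated reporting with no adverse-event question elsewhere in the available text. Some harms may go unrecorded. The size of the under-count is unknown: the 28%, 54% and 74% chances of recording nothing (n = 12) rest on an assumed 10% event proportion and assumed capture fractions, and show only how sensitive so small a sample is.

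The direction of bias in a baseline-versus-EFT comparison is also uncertain, because contact is much more frequent during EFT. The change is cheap and worth making. The conclusion assumes that the two unseen documents contain no routine adverse-event question.

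**What to change.** - **21.4:** add one scripted, open question about health problems and any change in medicines since the last contact. Ask it at every scheduled session and call in baseline and EFT. Record the answer (including none), the contact date and the onset date, so that an event starting in baseline but reported at the first EFT contact is assigned to baseline. Feed the answers into the existing weekly review. If the measures attachment already holds such an item, cite it here.
- **Reporting:** list events descriptively by phase, with the number of contacts and the recall interval. State that a difference in rates between baseline and EFT will not be read as an effect of EFT, because ascertainment is unequal.
- **23.1 and consent:** name increased drug effect from better adherence as a foreseeable risk.

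No change to the timing in 21.7 is needed for this point. Any clinical response to a reported event is for the investigators and prescribers to define.

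**Cost:** protocol and consent wording, and about one minute per contact (assumed). At the largest count, 16 EFT contacts plus three assessments, that is about 19 minutes per participant over the study. **Downside:** more minor events will be recorded, and ascertainment will remain unequal between phases even with the same question.
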